glucose levels will be measured using a colorimetric enzymatic assay, insulin levels will be quantified using a human-specific radioimmunoassay, and C-peptide levels will be determined through a chemiluminescent immunometric assay. Area under the curve (AUC), along with the Matsuda index (103), homeostatic model assessment-insulin resistance (HOMA-IR) and homeostatic model assessment of β -cell function cell function (HOMA-B) (104) will be calculated.

Telomere length

Particularly for telomere length (TL) analysis, blood samples will be collected using ethylenediaminetetraacetic acid (EDTA) tubes and stored at -80°C until analysis. DNA will be extracted using the PureLink™ Genomic DNA Mini Kit (Thermo Fisher Scientific) following the manufacturer's instructions. DNA will be quantified using the NanoVue Plus spectrophotometer (General Electric), and its integrity will be evaluated via gel electrophoresis technique (105, 106). TL analysis will be measured in accordance with the modified protocol described by Cawthon and colleagues (107). The relative average of telomeres will be quantified via Real-Time Polymerase Chain Reaction (RT-qPCR) technique. RT-qPCR reactions will be conducted in 96-well plates using the StepOnePlus™ Real-Time PCR System (Applied Biosystems®). All samples and reference DNA will be analyzed in duplicates using 25 ng of DNA. Three wells for internal control will be included in each run. For the reaction, the SYBR® Green PCR Mastermix kit (PureLink™) will be used with a final volume of 25 μ L. The specific primer sequences used for telomeres are presented in Table 2. The 36B4 reaction will include 12.5 μ L of SYBR Green (PureLink™), 0.03 μ L of forward primer, 0.05 μ L of reverse primer, and 11.42 μ L of ultrapure water. For the telomere reaction, 12.5 μ L of SYBR Green, 0.03 μ L of forward primer, 0.03 μ L of reverse primer, and 11.44 μ L of ultrapure water will be used. The RT-qPCR run will consist of four distinct steps: first, an initial step at 50°C for 2 minutes. Second, 40 amplification cycles at 95°C for 2 minutes each. Third, a step at 55°C for 15 seconds. Finally, a step at 60°C for 1 minute.

Table 2. Primer sequences and concentrations for telomere and 36B4 gene amplification in RT-qPCR Assay

Primer	Sequence (5' -> 3')	Concentration (nM)
Tel 1 Forward	GGT TTT TGA GGG TGA GGG TGA GGG TGA GGG TGA GGG T	300
Tel 2 Reverse	TCC CGA CTA TCC CTA TCC CTA TCC CTA TCC CTA TCC CTA	300
36B4u Forward	CAG CAA GTG GGA AGG TGT AAT CC	300
36B4d Reverse	CCC ATT CTA TCA TCA ACG GGT ACA A	500

The relative quantification of TL will be determined using the telomere to single-copy gene ratio (T/S) by calculating the delta values (Δ) of cycle threshold (Ct) [Ct (telomeres) - Ct (reference gene)]. Following the parameters previously described (108), the ratio of T/S for each sample will be calculated using the equation:

$$2 - \Delta\Delta CT = 2 - \Delta CT(\text{a target sample}) - \Delta CT(\text{a reference sample})$$

Health-related quality of life

Health-related quality of life (HRQoL) will be evaluated through the Medical Outcomes Study 36 – Item Short-Form Health Survey (SF-36) (109). The SF-36 provides scores across eight domains: physical functioning, role-physical, bodily pain, general health, vitality, social functioning, role-emotional, and mental health. Additionally, physical and mental component summary scores will be calculated. Scores will range from 0 to 100, with lower scores indicating worse HRQoL.

Sleep quality

Sleep quality will be assessed using the Portuguese version of the Pittsburgh Sleep Quality Index (PSQI) (110). In brief, the PSQI assesses sleep quality over a 1-month period by means of a questionnaire involving 19 self-rated questions and 5 questions answered by bedmates/roommates. The latter questions are used only for clinical information, and thus, will not be used in the current study. The 19 questions are categorized into 7 components, graded on a score that ranges from 0 to 3. The PSQI

components are as follows: subjective sleep quality (C1), sleep latency (C2), sleep duration (C3), habitual sleep efficiency (C4), sleep disturbances (C5), use of sleeping medication (C6) and daytime dysfunction (C7). The sum of scores for these 7 components will yield one global score, which will range from 0 to 21, in which the highest score indicates worst sleep quality. Participants will be classified as good sleepers in case of PSQI ≤ 5 and poor sleepers for PSQI > 5 .

Depression and anxiety

Depression will be assessed using the short form of the Geriatric Depression Scale (GDS) with 15 items (GDS-15), which is specifically designed for screening depression in older adults (111). This shortened version offers very similar sensitivity and specificity compared to the original 30-item scale (112). Each item on the abbreviated scale will be scored as either 0 or 1, resulting in a total score range from 0 to 15. A cutoff score between 5 and 6 will be used to differentiate between non-cases and cases of depression.

Anxiety will be assessed using the Geriatric Anxiety Inventory (GAI), a self-administered tool comprising 20 questions with dichotomous responses (agree/disagree) (113). This brief questionnaire will be easy to use even in cases of fatigue, lower education levels, or mild cognitive impairment. The GAI will employ a cutoff score system where scores between 0 and 10 will indicate absence of anxiety, scores between 11 to 15 will denote mild to moderate anxiety, and scores between 16 to 20 will be suggestive of severe anxiety.

Cognitive processing speed

Cognitive processing speed will be assessed utilizing the Trail Making Test (TMT). The most widely employed version of the TMT comprises parts A and B. In part A, the subject utilizes a pencil to connect a series of 25 encircled numbers in numerical order. In part B, the subject connects 25 encircled numbers and letters in numerical and alphabetical order, alternating between the numbers and letters. For instance, the first number "1" is followed by the first letter "A," followed by the second number "2" then second letter "B" and so forth. The numbers and letters are positioned in a semi-random fixed order, in such a manner as to prevent overlapping lines being drawn by the

examinee. The primary variables of interest are the total time to completion for parts A and B. A cutoff time of 300 s is generally employed to discontinue test administration and is therefore the typical maximum score (114).

Cognitive executive function

Cognitive executive function will be assessed by Stroop Test (ST) (Victoria version). The ST will follow the guideline specifications suggested by Duncan 2006 (115). Three cards, each containing 24 stimuli against a white background, will be used. Card A will consist of rectangles printed randomly in green, pink, blue, and brown. Card B will be organized similarly to Card A but will have rectangles replaced by unrelated words to concepts of color (each, never, today, and all) printed in uppercase in the four colors mentioned. Card C will also be organized similarly to Card A, representing the interference card where the written stimuli will be the names of the colors (brown, blue, pink, and green) printed in the same colors, ensuring that the ink color and the color name never match (e.g., the word "brown" printed in pink, green, or blue). For the first card, participants will state the colors of the rectangles as quickly as possible. For cards B and C, subjects will state the color of the printed words instead of reading the words themselves. The criterion score will be the time taken to perform the task for each card, and all errors will be corrected promptly without stopping the chronometer (116).

EXPERIMENTAL INTERVENTIONS

Caloric restriction and dietary supplementation

Participants allocated to the intervention groups (PTN and PLA) received individual meal plans to induce a caloric deficit of 300-500 kcal/day from their habitual energy intake assessed at baseline. Habitual intake values were contrasted with total energy requirements individually estimated by FAO/WHO equation for older adults, applying a sedentary activity factor at baseline and an active factor for later time points (differences between calculation methods were <1% throughout the study). The caloric deficit was maintained based on regular reassessment of dietary parameters every four weeks. In addition, participants met biweekly with registered dietitians for individual

behavioral therapy involving nutritional education in order to enhance adherence to the caloric restriction protocol.

Participants from PTN and PLA will be provided, on a weekly basis, with unlabeled dietary supplement bottles to be consumed daily at breakfast. The PTN group will receive 40g of whey protein (Nutrata®, São Paulo, Brazil), while the PLA group will receive an isocaloric non-nitrogenous placebo (Nutrata®, São Paulo, Brazil), consisting of a carbohydrate blend (isomaltulose, waxy maize, maltodextrin), with the same flavor (natural chocolate) and texture. They will be asked to record their supplement intake (time and day) and return the bottles (empty or not) weekly to monitor adherence. To ensure a daily intake of 1500mg of calcium and 1000IU of vitamin D, calcium and vitamin D supplements will also be provided to prevent deficiencies associated with caloric restriction, as previously recommended (117).

The research team will be available to answer any questions about the supplementation protocol throughout the trial.

Exercise training intervention

Participants from both PTN and PLA groups will engage in a three-times-a-week exercise training program for 16 weeks. The program will include resistance and endurance exercises. Resistance training will consist of six exercises targeting major muscle groups: incline leg press 45°, leg extension, leg curl, calf raise, horizontal bench press, and lat pull-down. Endurance training will involve walking and/or running. The exercise training protocol's periodization will follow recommendations from widely accepted position stands for older adults (118, 119) (Table 3). For each exercise, resistance training will progress from 1 set of 15-20 repetition maximum (RM) in the first week to 3 sets of 10-12 RM in the final four weeks of training. Whenever a participant exceeds the upper limit of the repetition range for two consecutive sets, the intensity will be adjusted by increasing the exercise load. Similarly, endurance exercise will progress from 30 minutes at 55–65% of heart rate maximum (HRmax) during the first four weeks to 40 minutes at 70–80% HRmax during the last four weeks of training. Borg's Rating of Perceived Exertion (RPE) scale (120) will be used as an auxiliary tool for monitoring exercise intensity and training progression. In these cases, the targeted intensity will range from 'very light'/'fairly light' (Borg's RPE score 9–11 a.u.) to 'somewhat hard'/'hard'

(Borg's RPE score 13–15 a.u.). All training sessions will be supervised by an experienced exercise physiologist blinded to the participants' group assignment. A training log will be maintained for each session to monitor adherence and control the training load.

Table 3. Exercise training prescription.

Type of exercise	Weeks	Volume	Intensity	Borg's RPE
Resistance training	1	1 set	15-20 RM	NA
	2-4	2 sets	15-20 RM	NA
	5-8	3 sets	15-20 RM	NA
	9-12	3 sets	12-15 RM	NA
	13-16	3 sets	10-12 RM	NA
Endurance training	1-4	30 min	55-65% HR _{max}	9-11 a.u.
	5-8	35 min	55-65% HR _{max}	9-11 a.u.
	9-12	40 min	60-70% HR _{max}	11-13 a.u.
	13-16	40 min	70-80% HR _{max}	13-15 a.u.

Abbreviations: RM: repetition maximum, HR_{max}: maximum heart rate, RPE: rating of perceived exertion, a.u.: arbitrary units, NA: Not applicable.

To address the higher prevalence of comorbidities in this population, additional precautions will be implemented. All participants will have their resting blood pressure measured by an automatic monitor (SPACELABS, São Paulo, Brazil) immediately before each training session, and sessions will be suspended if systolic or diastolic blood pressure readings are ≥ 160 mmHg or ≥ 105 mmHg, respectively (121, 122). Likewise, blood glucose levels will be measured before training sessions for participants with type-2 diabetes, with acceptable values considered to be between 90 and 250 mg/dL (123). Additionally, heart rate (HR) and peripheral oxygen saturation (SpO₂) will be continuously monitored during endurance exercise. Whenever necessary, participants will receive outpatient care and consultation with our medical staff.

The CON group will receive one-on-one guidance and behavioral orientations focusing on a healthy lifestyle, including nutritional education and physical activity at PRE, and every four weeks throughout the trial.

SAMPLE SIZE CALCULATION

Sample size was determined a priori using the G-Power software (Version 3.1.9.2, University of Kiel, Germany). The analysis was conducted by inputting α error (0.05), power ($1 - \beta$ error = 0.95), and effect size (Hedges' g = 0.61), considering previous data indicating a lower loss of fat-free mass in individuals undergoing caloric restriction who had an increase in protein intake compared to their counterparts who maintained their usual protein intake (31). Calculations were based on an ANOVA with repeated measures (within-between interactions) and the total sample size was determined to be 81 individuals. To account for midtrial withdrawals, the sample will be increased by ~30% (i.e. 105 participants).

DATA ANALYSIS

Data will be presented as mean \pm standard deviation (SD), estimated mean difference between groups (EMD) at POST (only in the presence of group x time interaction), 95% confidence interval (95%CI), unless otherwise indicated. Baseline characteristics will be compared between groups using either Fisher exact test or generalized linear model with Sidak post hoc adjustment whenever necessary. Data will be analyzed using an intention-to-treat (ITT) approach to preserve the integrity of randomization. Before inferential analysis, outliers will be identified, and the data will be tested for homogeneity of variance and sphericity. Dependent variables will be analyzed by a linear mixed model analysis for repeated measures (assuming time [PRE and POST] and group [PTN, and PLA] with baseline values as covariate. The restricted maximum likelihood method, compound symmetry covariance structure, and Kenward-Roger degrees of freedom approximation will be applied for all models. In order to maintain the overall significance level at 0.05, the primary endpoints will be assessed using Hochberg's procedure (124). For all secondary outcomes the significance level will be set at $p \leq 0.05$. Whenever significant group-by-time interactions are identified, post-hoc tests on the adjusted predictions with Sidak's adjustment will be performed for multiple comparisons.

All analyses will be performed in the statistical environment R (version 3.5.3; R Core Team 2020).

STATISTICAL ANALYSIS PLAN

All analyses will be performed in the statistical environment R (version 3.5.3; R Core Team 2020). We will perform all the comparisons using two-sided significance tests. Intention-to-treat analyses will be performed by analyzing data from all participants originally randomized to preserve the integrity of randomization. The longitudinal analysis of all outcomes will be performed using a linear mixed model for repeated measures, assuming 'group' (PTN, and PLA) and 'time' (pre-intervention and post-intervention) as fixed factors, and 'subjects' as a random factor, with an interaction between 'group' and 'time' added to the model; baseline values of the outcome will be used as covariates. For all models, maximum restricted likelihood and Kenward-Roger degrees of freedom will be used for model fit and estimation. We will adjust for testing of the four primary outcomes, total fat-free mass, appendicular fat-free mass, appendicular fat-free mass relative to body mass index, and leg fat-free mass, using Hochberg's procedure in order to maintain the overall significance level at 0.05. Since the other hypothesis tests (for the secondary outcomes) will be more exploratory in nature, the Hochberg's correction will not be used, and two-sided p-values less than 0.05 will be considered to indicate statistical significance. For both primary and secondary outcomes, whenever significant group-by-time interactions are identified, post-hoc tests on the adjusted predictions with Sidak's adjustment will be performed for multiple comparisons.

Mixed model analyses will be used instead of standard repeated measures analysis of variance because of the likelihood that there will be dropouts and missed visits that preclude the use of the classical approach (125, 126). The mixed model approach we will employ fits a linear regression model to each subject and assumes that both error terms and regression coefficients are normally distributed in these lines. It then uses the EM algorithm to combine the individual lines and to generate empirical Bayes, maximum likelihood, and restricted maximum likelihood estimates of model parameters. Because lines are generated for individuals, the model is more general than standard repeated measures analysis of variance in that it has no requirements about common measurement times between subjects and can deal easily with missing data. In all analyses, careful attention will be given to ensuring that the conditions that are required of a particular statistical method are satisfied. We will assess the normality of regression residuals and ensure the homogeneity of variances when analyzes of variance and covariance are performed. When required assumptions are not satisfied, data transformations will be explored and utilized as appropriate.

STUDY TIME LINE

July 2021 – August 2023

REFERENCES

1. Roh E, Choi KMJFie. Health consequences of sarcopenic obesity: a narrative review. 2020;11:530178.
2. Wannamethee SG, Atkins JLJCDR. Sarcopenic obesity and cardiometabolic health and mortality in older adults: a growing health concern in an ageing population. 2023;23(11):307-14.

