This will be a single-center, double-blinded, parallel-group, randomized, placebo-controlled trial. Older adults with sarcopenic obesity (n= 105) will be allocated to one of three groups: protein supplementation (PTN, n=35), placebo supplementation (PLA, n=35), or control (CON, n=35). The PTN and PLA groups will receive dietary supplements in addition to an exercise training and calorie restriction intervention, while the CON group will receive no intervention. Body composition, bone health, cardiorespiratory fitness, pulmonary function, functional capacity, muscle cross-sectional area, upper and lower-limb maximal dynamic strength, endothelial function, biochemical parameters, health-related quality of life, cognitive function, sleep quality, symptoms of anxiety and depression, and nutritional status will be assessed before and after a 16-week intervention period. A linear mixed model with repeated measures analysis will be conducted to assess within- and between-group effects of the intervention, using baseline values of the outcome as covariates. Whenever significant group-by-time interactions will be found, post-hoc tests on the adjusted predictions with Sidak's adjustment will be performed for multiple comparisons. Significance will be set at $p<0.05$. Data will be reported as the mean and standard deviation, along with the estimated mean difference (EMD) between groups and its 95% confidence interval (95% CI) when a main effect or interaction is observed.

BACKGROUND AND SIGNIFICANCE

The prevalence of obesity among older adults is growing worldwide (1-3). Excessive adipose tissue is linked to insulin resistance, high blood pressure, endothelial dysfunction, and dyslipidemia, obesity offers a heightened risk for developing cardiovascular and metabolic diseases, particularly among older individuals (4-6). Concurrently, aging is associated with declines in skeletal muscle mass and function (i.e., sarcopenia) (7), which can be further exacerbated by obesity (8-10). The interplay of these conditions poses an emergent public health issue termed sarcopenic obesity (11-13), a condition associated with greater risk of morbimortality and worse health-related quality of life (14, 15).

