Men and women aged 65 years or older, with central obesity (waist circumference >102 cm for men and >88 cm for women), body mass index (BMI) of ≥ 30 kg/m², sarcopenia (according to the criteria set by the Foundation for the National Institutes of Health (FNIH) (68)), not engaged in an exercise training program, and with stable weight within the past 6 months will be considered eligible to participate. Reference cut-off values for sarcopenia will include a handgrip strength-to-BMI ratio of less than 1.0 kg/BMI and an appendicular fat-free mass-to-BMI ratio of less than 0.789 kg/BMI for men, and a handgrip strength-to-BMI ratio of less than 0.56 kg/BMI and an appendicular fat-free mass-to-BMI ratio of less than 0.512 kg/BMI for women (68).

Exclusion criteria

Exclusion criteria will include a history of recent malignancies (within the past 5 years); cognitive deficits or dementia that prevent the participant from reading and signing the informed consent form; and medical conditions in which physical testing or engaging in exercise training would be contraindicated (e.g., locomotor disabilities or cardiopulmonary diseases, including unstable angina, heart failure, myocardial infarction, or chronic obstructive pulmonary disease).

Follow-up procedure:

In case of drop-out, the participant will be asked to complete a full set of examinations at the time of drop out.

STUDY DESIGN

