The present study will be a single-center, double-blinded, parallel-group, randomized, placebo-controlled trial. Figure 1 illustrates the study design. Initially, participants will be pre-screened through phone calls or personal interviews. Those who meet the preliminary criteria will then be further assessed for their medical condition and eligibility criteria. Eligible participants will be matched based on sex and then randomly allocated in a 1:1:1 ratio into one of the following experimental groups: (a) protein supplementation (PTN), (b) placebo supplementation (PLA), or (c) control (CON). Both the PTN and PLA groups will receive dietary supplementation, will be caloric-restricted, and will engage in an exercise training program. Participants in the CON group will receive no intervention other than general guidance on healthy eating and physical activity. All outcomes of interest will be assessed immediately before participants' randomization at baseline (PRE) and after 16 weeks of intervention (POST). Anthropometric and dietary parameters will be reassessed at weeks 4, 8, and 12. Participants will also meet with a registered dietitian from the research team every two weeks in order to ensure compliance with the dietary intervention.

RANDOMIZATION

Eligible participants will be sex-matched and then randomly allocated using a computer-generated block design in a 1:1:1 ratio into one of the following experimental groups through a specific software (<https://randomizer.org>): (a) protein supplementation (PTN), (b) placebo supplementation (PLA), or (c) control (CON). The allocation sequence will be concealed from the research staff.

EXAMINATIONS

The primary outcome will be the change from baseline in fat-free mass (total, appendicular, appendicular relative to BMI and leg). Secondary outcomes will include other measures of body composition (i.e. fat and bone density), bone microarchitecture, bone metabolism, and specific muscle functions. Other outcomes, including cardiopulmonary capacity (cardiorespiratory fitness and pulmonary function), glycemic control, insulin sensitivity, endothelial function, inflammation, cognitive function and

related cellular and molecular mechanisms (telomere length, oxidative stress, and lipid profile) will also be assessed.

Anthropometry

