insufficient extraction of the cortex, which may be thin and/or highly porous, or when the trabecular structure is rich and well connected to the cortex), the advanced analysis method, also known as the extended analysis, will be used for the determination of cortical parameters (cortical vBMD, Ct.Th, and Ct. Po) (79).

For the analyses of volumetric density and structural parameters, the analysis of FE models of the distal radius will be carried out based on images obtained directly from HR-pQCT, with the aim of evaluating the biomechanical parameters of the bone and, therefore, estimate tissue susceptibility to fractures. For FE analysis, the software provided by the equipment manufacturer will be used (Finite Element Software, v.1.13, Scanco Medica AG, Switzerland, January 2009, Manufacturer's Guide). The vector information obtained from the models will be converted into blocks called voxels, which comprise the smallest unit that makes up the image of the analyzed material and have a cubic format. In FE analysis, the software will estimate and analyze the behavior of bone tissue when it is subjected to a force along its axis.

Bone mineral content and areal bone mineral density

Bone mineral content (BMC) and areal bone mineral density (aBMD) will be assessed by whole-body DXA using a Hologic QDR 4500A densitometry equipment (Discovery Densitometer, Hologic Inc., Bedford, MA, USA). The aBMD will be measured at the following sites: lumbar spine (L1 to L4), femoral neck, total hip, and whole body in accordance with the recommendations from the International Society for Clinical Densitometry (81).

Strength and functionality

Isometric strength

Isometric handgrip strength will be obtained using a handgrip dynamometer (Jamar®, Sammons Preston Rolyan, USA). The test will be conducted with the participant seated, shoulders adducted, and in a neutral rotation with their elbow bent at a 90° angle (82). They will perform three maximum effort attempts, each lasting 5 seconds, with a 1-minute rest interval between each attempt. The best result will be recorded for analysis.

Isoinertial strength

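### The Summary treats within-arm PRE-POST change as an effect of the intervention, although entry selects on a primary outcome and the model has no control arm

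*Combined protocol and SAP*

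**What the plan says.** The Summary of Study sets the aim of the analysis: "A linear mixed model with repeated measures analysis will be conducted to assess within- and between-group effects of the intervention". It adds that the between-group estimated mean difference (EMD) will be reported "when a main effect or interaction is observed".

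Under Inclusion criteria, sarcopenia is defined by a grip/BMI cut-off together with "an appendicular fat-free mass-to-BMI ratio of less than 0.789 kg/BMI for men", and by "a handgrip strength-to-BMI ratio of less than 0.56 kg/BMI and an appendicular fat-free mass-to-BMI ratio of less than 0.512 kg/BMI for women". Participants must also have a BMI of at least 30 kg/m² and a waist above a sex-specific limit.

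Some of these quantities return as outcomes. Examinations states: "The primary outcome will be the change from baseline in fat-free mass (total, appendicular, appendicular relative to BMI and leg"). The Statistical Analysis Plan repeats "appendicular fat-free mass relative to body mass index" among its four primary outcomes. Under Isometric strength, "Isometric handgrip strength will be obtained using a handgrip dynamometer", and strength is a secondary outcome in the Aim.

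Study Design places outcome assessment before "randomization at baseline (PRE) and after 16 weeks of intervention (POST"). It does not say whether PRE is measured afresh or reuses the value that qualified the participant.

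Data Analysis and the Statistical Analysis Plan specify a mixed model with group, time and their interaction. In both, the group factor has two levels, PTN and PLA. Post-hoc tests with Sidak's adjustment follow only a significant interaction.

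**The concern.** People admitted because a measured value was low tend to show a higher value next time, with no treatment at all. Those admitted for a high BMI or waist tend to show a lower one. Both movements look like benefit in this trial. Randomisation balances them between arms, but nothing removes them from the change within one arm. The baseline covariate does not help either: it adjusts the comparison between arms and leaves the average PRE-POST shift where it is.

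The stake is the claim about the package. The last sentence of Background and Significance hypothesises benefits of the integrated approach, not only of protein. A statement that fat-free mass/BMI or strength improved with diet and training would rest on PRE-POST change in PTN and PLA, because the model contains no CON arm to show what happens without the package.

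**Working it through.** The plan gives no figure for this, so there is none to reproduce. The mechanism can be sized.

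**Inputs from the documents.** 35 randomised per arm; two-sided 0.05; entry by an upper cut-off on appendicular fat-free mass/BMI.

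**Assumptions (not in the documents).** The qualifying value is used as PRE. A share q = 0.20-0.30 of the source population lies below the cut-off. The untreated PRE-POST correlation is r = 0.90-0.99. There is no true change.

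**Formulas, in population SD units.** With z the q-quantile of the standard normal:
- mean PRE below the population mean: λ = φ(z)/q
- spurious shift: (1 − r)λ
- variance of PRE among those selected: v = 1 − zλ − λ²
- SD of change: √[(1 − r)²v + 1 − r²]
- rejection rate of a paired test: noncentral t, 34 df, noncentrality √35 × shift/SD

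**One case in full (q = 0.20, r = 0.90).** z = −0.842 and φ(z) = 0.280, so λ = 0.280/0.20 = 1.40. Shift = 0.10 × 1.40 = 0.14. v = 1 + 0.842 × 1.40 − 1.40² = 0.219. SD of change = √(0.01 × 0.219 + 0.19) = 0.438. Standardised shift = 0.14/0.438 = 0.319; noncentrality = 5.916 × 0.319 = 1.89; rejection 45%.

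**Ungated single-arm test, n = 35**

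| r | Shift, q = 0.30 to 0.20 (SD) | Rejection rate |
|---|---|---|
| 0.90 | 0.12 to 0.14 | 33% to 45% |
| 0.95 | 0.06 to 0.07 | 19% to 25% |
| 0.98 | 0.02 to 0.03 | 10% to 13% |
| 0.99 | 0.01 | 8% to 9% |

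If the time main effect over PTN and PLA together (n = 70) were read as an effect, the same calculation gives 33-75% at r = 0.90-0.95 and 16-21% at r = 0.98.

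**Randomised comparison under the same selection.** Simulated false-positive rates for PTN against PLA were 4.2-4.8% for the interaction and 4.4-4.8% for ANCOVA. The shift cancels.

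**Effect of the interaction gate.** With no true change, a significant interaction together with any Sidak-adjusted within-arm result occurred in about 2-5% of simulated trials for r = 0.90-0.98.

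**If PRE is a fresh measurement.** With independent errors at qualification, PRE and POST (r = 0.90, q = 0.20), single-arm rejection was 5.2%. The regression has already happened by PRE.

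**The case against.** The strongest reply is that the operative plan does not do this. The within-group wording occurs only in the Summary. Data Analysis and the Statistical Analysis Plan test the interaction, report a between-group difference at POST, and gate every post-hoc test. That is correct, and it is why the problem is limited: when there is no true effect, the gate keeps post-hoc within-arm findings at or below about 5%.

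The reply does not dispose of the point. The time main effect is a fixed term that the gate does not cover, and the Summary's wording invites reading it as an effect. Once a real protein effect produces a significant interaction, the gate is open. The plan does not say which contrasts form the Sidak family, and within-arm changes plausibly belong to it.

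Four stronger readings are tempting, but the documents do not support them.
- That the protein comparison is biased: it is not, as the simulated error rates show.
- That the Summary's mention of a main effect shows that PRE-POST tests are planned: that clause completes a sentence about the EMD between groups.
- That the sponsor will contrast a significant change in PTN with a non-significant one in PLA: no section proposes this, and the interaction test is the proper alternative.
- That the 19-45% is the trial's error rate: it belongs to ungated tests under assumed correlations and reuse of the qualifying value.

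Two limits also stand. Handgrip is recorded as strength, while selection acts on grip/BMI, so the calculation applies less directly to it. Total and leg fat-free mass are not entry variables and are affected only indirectly.

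**Conclusion.** The point holds in a limited form. A PRE-POST change within an arm cannot be called an effect of the intervention in a group selected on appendicular fat-free mass/BMI, grip/BMI, BMI and waist. The stated model also offers no control reference for the diet-plus-training package. The main test of protein is sound.

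The magnitude cannot be fixed from the documents. It runs from close to nil (fresh PRE with independent error), through 0.01-0.03 SD (retest correlation 0.98-0.99), to 0.06-0.14 SD (0.90-0.95). The last two ranges require that the qualifying value serves as PRE and that 20-30% of the source population qualifies. Other time trends would come on top and are not sized here. The change is worth making because it is cheap and closes off a claim that the design cannot support, not because the primary result is in doubt.

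**What to change.** 1. In the Summary, limit the stated target of the mixed model to between-group effects.
2. Report PRE-POST change in each arm descriptively: mean change with 95% CI, no p-value and no effect wording. State that the Sidak family contains between-group contrasts only.
3. State that conclusions about protein rest on PTN minus PLA.
4. State that any conclusion about diet plus training rests on contrasts with CON, and add CON to the group factor in both Data Analysis and the Statistical Analysis Plan. With three levels, a significant interaction could come from CON alone, so PTN minus PLA should be named as its own prespecified contrast and carry the Hochberg procedure for the four primary outcomes.
5. State whether PRE is a fresh measurement or the qualifying one.

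Cost: within-arm p-values are given up, and the model gains a third group level with the extra contrasts that follow. This is more than a wording change, but it needs no new data and no change to the sample size, since CON is already randomised and measured.
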